10.1 Disposition of Subjects and Discontinuations

This following will be presented in a summary table:

- Total number of subjects screened (ie, subjects who gave informed consent)
- Number of screened subjects who discontinued from the trial prior to treatment overall and grouped by the main reason for discontinuation:
 - Subject did not meet all eligibility criteria
 - Withdrew consent
 - Other
- Number of treated subjects
- Number and percentage of treated subjects who completed study
- Number and percentage of treated subjects who discontinued the study, with the primary reason of discontinuation:
 - Adverse event
 - Lost to follow-up
 - Protocol non-compliance
 - Death
 - Withdrew consent
 - Other
- Number and percentage of subjects who completed period (for periods 1 and 2)

- Number and percentage of subjects who discontinued study in period and reason for discontinuation (for periods 1 and 2)

A listing of discontinued subjects will be provided.

10.2 Protocol Deviations

10.2.1 Important Protocol Deviations

Listings of important protocol deviations will be provided including the date and relative day in relation to dosing in the relevant period.

10.2.2 Reasons Leading to the Exclusion from an Analysis Set

All criteria/reasons leading to the exclusion of a subject from an analysis set will be listed based on the safety set.

Reasons for excluding individual PK concentrations will also be listed separately and flagged in the main listing based on the safety analysis set.

11 Demographics and Other Baseline Characteristics

11.1 Demographics

Summaries will be given for both the safety and the pharmacokinetic set, if different.

Demographic characteristics will be listed by subject and summarized using the following information from the Screening/Baseline Visit eCRF pages.

Demographic characteristics:

- Sex: male, female
- Race: Black or African American, American Indian or Alaska Native, Asian, Native Hawaiian or Pacific Islander, White, Other
- Ethnic origin: Hispanic or Latino, Not Hispanic or Latino, Japanese, Not Japanese
- Age (years): summary statistics
- Height (cm) at Baseline: summary statistics
- Weight (kg) at Baseline: summary statistics

- BMI (kg/m²) at Baseline: summary statistics

Age will be taken from the eCRF and cannot be derived from the data because only the year of birth is collected in the eCRF.

BMI will be re-derived (ie, not taken directly from the database) according to the following formula:

- BMI (kg/m²) = weight (kg) / (height (m) * height (m))

11.2 Medical History

The medical history will be listed by subject including the preferred term and MedDRA system organ class (SOC) body using MedDRA, current version.

11.3 Other Baseline Characteristics

Other baseline characteristics will be listed by subject and summarized using the following information from the Screening/Baseline Visit eCRF pages.

Other baseline characteristics:

- Smoking status
- Alcohol consumption

12 Previous or Concomitant Medications/Procedures

Previous medications are medications, other than trial medications and pre-medications for trial drug, which started and stopped before first administration of trial drug.

Concomitant treatments are medications, other than trial medications, which are taken by subjects any time on-trial (on or after the first day of trial drug treatment for each subject).

In case the date values will not allow to unequivocally allocating a medication to previous or concomitant medication the medication will be considered as concomitant medication

Any previous and concomitant medication will be encoded with WHO-DD, latest version. Prior and concomitant medications will be listed by subject (all subjects).

The following information will be displayed in a listing: generic or trade name (as reported in eCRF), WHO drug name (including ATC-2nd level and preferred term), dose/unit, route, frequency, reason for use, start/end date and time.

Concomitant procedures will be presented in a data listing.

13

Treatment Compliance and Exposure

A listing of date and time of each drug administration and each blood sampling including time deviations will be provided sorted by subject.

14

Efficacy Analyses

Not applicable.

15

Safety Analyses

The subsections in this section include specifications for summarizing safety endpoints that are common across clinical trials such as adverse events, laboratory tests and vital signs.

Safety data analysis will be conducted on the Safety Analysis Set.

15.1

Adverse Events

The number and percentage of subjects experiencing at least one TEAE will be summarized by treatment as well as the number of events. A TEAE is an AE with onset after start of treatment. Tables by relationship to trial drug and by severity will be generated. AEs will be coded using Medical Dictionary for Regulatory Activities terminology, latest version.

Incomplete TEAE-related dates will be handled as follows:

- In case the onset date is missing completely or missing partially but the onset month and year, or the onset year are equal to the start of trial treatment then the onset date will be replaced by the minimum of start of trial treatment and TEAE resolution date.
- In all other cases the missing onset day or missing onset month will be replaced by 1.
- Incomplete stop dates will be replaced by the last day of the month (if day is missing only), if not resulting in a date later than the date of subject's death. In the latter case, the date of death will be used to impute the incomplete stop date.
- In all other cases the incomplete stop date will not be imputed.

15.1.1

All Adverse Events

All AEs recorded during the course of the trial (ie, assessed from signature of informed consent until the end of the Follow-up/End of Trial visit) will be coded according to MedDRA latest version and assigned to a SOC and PT.

TEAEs will be summarized by worst severity, using MedDRA latest version preferred term as event category and MedDRA primary system organ class (SOC) body term as Body System category. The severity of AEs will be graded using the “National Cancer Institute - Common Terminology Criteria for Adverse Events” (NCI-CTCAE) guideline, as detailed in the study protocol.

TEAEs related to trial treatment are those events with relationship missing, unknown or related.

The following will be summarized in an overview table with the number and percentage of subjects (and the number of events) by treatment and overall:

- Any TEAE
- Any trial treatment related TEAE
- Any TEAE related to dabigatran
- Any TEAE related to tepotinib
- Any serious TEAE
- Any trial treatment related serious TEAE
- Any dabigatran related serious TEAE
- Any tepotinib related serious TEAE
- Any severe TEAE (grade ≥ 3)
- Any trial treatment related severe TEAE (grade ≥ 3)
- Any dabigatran related severe TEAE (grade ≥ 3)
- Any tepotinib related severe TEAE (grade ≥ 3)
- Any TEAE leading to death
- Any trial treatment related TEAE leading to death
- Any dabigatran related severe TEAE leading to death
- Any tepotinib related severe TEAE leading to death

TEAEs will be summarized by treatment and overall in tables with:

- The number and percentage of subjects by treatment with at least one TEAE and the number of events overall and by SOC and PT.
- The number and percentage of subjects by treatment with at least one non-serious TEAE and the number of non-serious TEAE applying frequency threshold of 5%.

Group/SOC terms will be sorted alphabetically and PTs within each group/SOC term will be sorted by descending frequency (based on all treatment groups combined).

In addition the following tables will be provided:

- A table by severity of TEAEs with the number and percentage of subjects by treatment with at least one TEAE and the number of events by SOC and PT.
- A table by relationship to trial treatment with the number and percentage of subjects by treatment with at least one TEAE and the number of events by SOC and PT.

Group/SOC terms will be sorted alphabetically and PTs within each group/SOC term will be sorted by descending frequency (based on all treatment groups combined)

Pre-treatment AEs (AEs with onset after informed consent but before start of treatment) and TEAEs will be listed separately.

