**Investigational Medicinal Product: dose/mode of administration/ dosing schedule:**

Tepotinib film-coated tablet (Tablet Formulation 2, TF2) containing 500 mg of drug substance, oral administration.

Dabigatran etexilate 75 mg hard capsules, provided as mesilate salt.

Period 1: A single oral dose of 75 mg dabigatran etexilate will be administered together with 240 mL of water in the morning of Day 1 of Period 1, 30 minutes (min) after start of a standardized breakfast (which must be consumed completely within 25 min).

Period 2: Single doses of 500 mg tepotinib will be administered together with 240 mL of water in the morning of Days 1 to 7 of Period 2, 30 min after start of a standard breakfast (which must be consumed completely within 25 min).

On Day 8 of Period 2, 500 mg tepotinib and 75 mg dabigatran etexilate will be administered together with 240 mL of water 30 min after start of the breakfast (which must be consumed completely within 25 min).

**Reference therapy: dose/mode of administration/dosing schedule:** Not applicable

**Planned trial and treatment duration per subject:** About 7 weeks from Screening to End of Trial Visit, treatment on Day 1 of Period 1 and Days 1 to 8 of Period 2.

**Statistical methods:** A general linear model with TREATMENT and SUBJECT as fixed effects will be applied to log-transformed PK parameters  $C_{max}$ ,  $AUC_{0-t}$ , and  $AUC_{0-\infty}$  of dabigatran (measured as total dabigatran) based on the PK analysis set. Treatment differences on the log scale of dabigatran with tepotinib vs dabigatran alone will be estimated for  $C_{max}$ ,  $AUC_{0-t}$ , and  $AUC_{0-\infty}$  together with their 90% confidence intervals (CIs). Point estimates and CIs will be back-transformed to the original scale.

Individual estimates of relative bioavailability of dabigatran will be calculated for each subject.

Summary statistics will be provided for all parameters.

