**Table 2 Schedule of Assessments - Period 2 (Administration of Tepotinib and Dabigatran Etexilate)**

Assessment/ Activity	Study Period 2							End of Trial Visit a
	Day 1	Day 2 - 6	Day 7	Day 8	Day 9	Day 10	Day 11	
Hospitalization	X	X	X	X	X	X	X j	
Ambulatory Visits								X
Physical examination								X
Vital signs (blood pressure, pulse rate, body temperature)	X b	X b	X b	X c	X c	X c	X c	X
12-lead ECG	X d	X						
Clinical laboratory (hematology, biochemistry, urinalysis)	X e	X e	X e	X e			X e	X
Coagulation	X i			X i	X i			X
Serum pregnancy test								X
Administration of tepotinib	X f	X f	X f	X f				
Administration of dabigatran etexilate				X f				
PK blood sampling (tepotinib and its metabolites)		X g	X g	X g				
PK blood sampling total dabigatran (unconjugated and conjugated)				X h	X h	X h	X h	
Adverse events	←-----→							X
Concomitant medication	←-----→							X

ECG = electrocardiogram, PK = pharmacokinetics

**Adverse events and concomitant medication will be assessed from screening throughout the whole study until End of trial Visit.**

- a 7 ± 1 days after last drug administration in Period 2 (Day 15).
- b Vital signs (blood pressure and pulse rate) will be measured after at least 5 min rest before each (within 60 min prior to dosing) and 6 h after each tepotinib administration.
- c Vital signs will be measured after at least 5 min rest before (within 60 min prior to dosing) as well as 4, 8, 24, 48 and 72 h after the combined dabigatran etexilate and tepotinib administration.
- d After at least 5 min rest before each time point 12-lead ECGs will be recorded and printed out. Days 1 to 7 within 60 min prior to dosing and 6 h after each tepotinib administration. Day 8 within 60 min prior to dosing, as well as 4, 8, 24, 48 and 72 h after the combined dabigatran etexilate and tepotinib administration.
- e Laboratory assessments will be performed on Day 1, 2, 7 and 8 pre-dose, and on Day 11.

- f On Days 1 to 7, 500 mg tepotinib will be administered together with 240 mL of water 30 min after start of a standardized breakfast (completely consumed within 25 min).  

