## **5 Investigational Plan**

### **5.1 Overall Trial Design and Plan**

This is a Phase I, open-label, single-sequence, 2-period, crossover study to investigate the effect of tepotinib on the PK of the P-gp probe substrate dabigatran etexilate determined from concentrations of total dabigatran (unconjugated plus conjugated) in 20 healthy subjects. A flowchart summarizing the overall study design is shown in [Figure 1](#).

The study will be divided into 2 periods: Period 1 will evaluate the PK of total dabigatran after single dose administration of 75 mg dabigatran etexilate (Pradaxa®, given as mesilate) over a sampling period 72 h post-dose, which covers > 5 times the geometric mean  $t_{1/2}$  of 8.4 h [1]. In Period 2, tepotinib will be administered for 7 days and the PK of tepotinib and its metabolites will be evaluated on Day 7. On Day 8, dabigatran etexilate and tepotinib will be co-administered and the PK of total dabigatran will be evaluated again over 72 h post dose. Dosing will be performed 30 min after start of a standardized breakfast (completely consumed within 25 min). Considering that in Period 2 dabigatran etexilate will be administered on Day 8 (= 168 h), the resulting interval between the 2 administrations of dabigatran etexilate will be 240 h (= 72 h [Day 1 to Day 4 of Period 1] + 168 h [Day 1 to Day 8 of Period 2]) or 10 days (see [Figure 1](#)).

A Screening period will occur from Day -28 to Day -2.

The subjects will be admitted to the study site on Day -1. They will be resident at the study site under medical supervision from Day -1 of Period 1 until Day 11 of Period 2.

Blood and urine samples will be collected for laboratory assessments (hematology, coagulation, biochemistry, urinalysis), which will be performed at Screening, throughout the inpatient period of each treatment period as explained in detail in Table 1 and Table 2 (also see Figure 1) and for the End of Trial Visit.

Serial blood samples for PK assessments will be collected for 72 h after administration of 75 mg dabigatran etexilate (Pradaxa®, given as mesilate) in Periods 1 and 2. Tepotinib PK will be assessed in Period 2.

The End of Trial Visit is planned 7 days ( $\pm$  1 day) after the last drug administration in Period 2 (Day 15  $\pm$  1). An Early Termination Visit will be conducted for subjects who withdraw prematurely. The same assessments as for the End of Trial Visit will be conducted at the Early Termination Visit.

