**Figure 1** **Study Design**

	Period 1			Period 2			End of Trial Visit Day
	Study Day			Study Day			
	-1	1	2 – 4 a	1 - 6	7	8	9 - 11
Dabigatran etexilate administration		↑				↑	
Tepotinib administration				↑↑↑↑↑↑↑↑	↑	↑	
PK blood sampling total dabigatran			↔			↔	
PK blood sampling tepotinib and its metabolites				X b	↔	↔	
Safety assessments			↔↔↔↔↔↔↔↔		↔↔↔↔↔↔↔↔		X c
Hospitalization			↔↔↔↔↔↔↔↔		↔↔↔↔↔↔↔↔		

a Day 4 of Period 1 = Day 1 of Period 2.

b PK sample prior to dosing on Day 6.

c End of Trial Visit safety assessments

A detailed schedule of study procedures and assessments is provided in Table 1 and Table 2.

Since to date tepotinib 500 mg was administered to healthy subjects only as single doses (study EMR200095-007, single dose; study MS200095-0012, 2 single doses), the safety and tolerability as well as the PK of multiple dose tepotinib (up to Day 8 inclusive in Period 2) will first be assessed in a subgroup of 6 subjects, followed by group(s) of the remaining subjects. Dosing of the subsequent group(s) will only be started if the safety and tolerability of multiple dosing of tepotinib was assessed as reasonable and no stopping rules applied. The decision will be documented and will be filed in the trial documentation files.

Stopping rules of the study:

- Further dosing will be temporarily stopped after occurrence of an SAE. Dosing will only be restarted if further investigation of the SAE clearly demonstrates another plausible scientific reason for the SAE other than the study drug.
- The trial will be permanently stopped if 4 or more subjects were withdrawn from the study because they fulfill the individual stopping criteria as defined in Section [5.5.2](#).
- Dosing will be permanently stopped if clinically relevant TEAEs of moderate or severe intensity of similar nature occur in at least 50% of subjects which are considered related to the study drug by the Investigator.

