For demographic, baseline and safety assessments, continuous measurements will be summarized by means of descriptive statistics (ie, number and percentage of observations, number and percentage of missing observations, mean, standard deviation [SD], median, 25th and 75th percentiles [Q1 and Q3], minimum, and maximum) and categorical data will be summarized by means of frequency tables (ie, count and percentages), if not stated otherwise. Mean, Median, Q1, Q3, Min, Max will have the same precision as the SDTM data (decimal places). SD will be presented with one decimal place more than the mean. Unless otherwise stated the calculation of proportions will be based on the number of subjects at risk or with available measurements in the analysis set of interest for safety outputs. For subject disposition and demographic tables the denominator will be the number of subjects in the analysis set. Counts of missing observations will be included as a separate category.

If not otherwise specified, 'baseline' refers to the last scheduled measurement before administration of the first drug in each period. However, if a subject is missing the baseline collection, the previous non-missing evaluation could become the baseline value (e.g. from screening/admission). If no baseline or previous to baseline evaluations exist then the baseline value will be treated as missing.

The following calculations and derivations, as applicable, will be used:

- Change from baseline: post-baseline visit value - baseline value
- Duration of AE (in days hh:mm) = end date and time - start date and time of the AE, if missing time for either the beginning or end then = end date – start date + 1
- Days hh:mm from dosing = start date and time of the event - date and time dose administration; (for treatment- emergent AEs), if missing time for either the beginning or end then = end date – start date + 1
- Rel. Day in study of AE = start date of the event – date of First Admin + 1 (for AEs on or after the day of dosing)
- Rel. Day in study of AE = start date of the event – date of First Admin (for AEs before the day of dosing)

Repeated laboratory assessments will be flagged as repeats in the subject data listings and not included in summary tables statistics (unless the scheduled measurement was considered unreliable, e.g. due to technical reasons, and needed to be replaced by an unscheduled repeat measurement).

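### SAP 15.1 gives undated Period 2 adverse events a Period 1 onset, and the SAP 9 missing-time fallback for days from dosing computes AE duration instead

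*SAP*

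**What the plan says.** **Onset imputation (SAP 15.1).** If the onset date is missing altogether, or is partial and its known month and year (or year) match the start of trial treatment, it is "replaced by the minimum of start of trial treatment and TEAE resolution date". For the rest, "In all other cases the missing onset day or missing onset month will be replaced by 1".

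**TEAE definition (SAP 15.1).** "A TEAE is an AE with onset after start of treatment". Worsening is not mentioned, and there is no start date per period. TEAEs are tabulated by treatment. SAP 9 lists two treatment labels, dabigatran and dabigatran + tepotinib. No section says how an event is assigned to one of them.

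**Time from dosing (SAP 9).** The main formula is event start minus dose time. When a clock time is missing, the fallback is: "if missing time for either the beginning or end then = end date – start date + 1". The line above it, for AE duration, has the same fallback in the same words.

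**Treatment order (Protocol, Synopsis and 5.1).** Subjects receive "treatment on Day 1 of Period 1 and Days 1 to 8 of Period 2". The first of these doses is dabigatran etexilate alone; tepotinib begins in Period 2.

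**The concern.** The imputation rule uses one anchor for the whole trial, although the trial has two treatment periods in a fixed order. An event that arose in Period 2 also resolved in Period 2 or later, so the earlier of the two candidate dates is always Period 1 Day 1. The event is then dated before any tepotinib was given. Elsewhere the SAP does work by period: SAP 9 sets baseline before the first drug in each period.

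The time-from-dosing fallback looks like text carried over from the duration line. Read that way, it reports how long the event lasted, not how long after the dose it began.

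The safety of tepotinib alone and with dabigatran etexilate is a secondary objective, and the protocol says this is the first multiple dosing of tepotinib in healthy subjects. Onset rules that can favour the tepotinib period should not be left in the plan, even if they are rarely used.

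**Working it through.** **Timeline.** Protocol 5.1 says "the resulting interval between the 2 administrations of dabigatran etexilate will be 240 h". Check: 72 h + 168 h = 240 h = 10 days, which agrees. Figure 1 adds "Day 4 of Period 1 = Day 1 of Period 2". Counting the first dose as study day 1, the minimum schedule is:

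- study days 1–3: dabigatran alone
- study days 4–10: tepotinib alone (Period 2 Days 1–7)
- study day 11 onward: co-administration and follow-up
- End of Trial Visit, Period 2 Day 15 ± 1: study days 17–19

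Tepotinib has started on 14/17 = 82% to 16/19 = 84% of these days, yet every undated onset goes to study day 1.

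**Imputation rule as written.** Take first-dose dates 1 January to 30 June 2018 (planned period Q1–Q2 2018; equal weight per date is my assumption) and true onsets on study days 4–18. That gives 181 × 15 = 2,715 combinations.

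- *No date, or year only:* the result is always study day 1, so 2,715/2,715 = 100% land in Period 1.
- *Month and year known:* an onset k days after the first dose (k = 3 to 17) falls in the next month for exactly k first-dose dates per month. Per month that is 3 + 4 + … + 17 = 150 combinations, and 6 × 150 = 900 over six months. The other 2,715 − 900 = 1,815 go to study day 1. Of the 900, those with a first dose on the last or second-last day of a month are set to the first of the next month, which is study day 2 or 3: 2 × 15 × 6 = 180. Total in Period 1: 1,815 + 180 = 1,995, and 1,995/2,715 = 73%.

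**Direction.** For any event with a true onset on or after the first dose, both candidate dates (treatment start, first of the month) are no later than the true onset. A Period 1 event therefore cannot move to Period 2. Running the rule over 181 × 3 = 543 Period 1 onsets gave 0 moves.

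**Time-from-dosing fallback.** Example: dose on Period 2 Day 8, onset on Day 9 with no clock time, end on Day 12.

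- Onset date minus dose date: 9 − 8 = 1 day (2 with +1).
- Fallback on the AE's own dates: 12 − 9 + 1 = 4 days, which is the AE duration.

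**Size in a table.** One subject of 20 is 1/20 = 5 percentage points.

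**The case against.** **The trigger should be rare.** Subjects are resident from Day -1 of Period 1 to Day 11 of Period 2 and are asked regularly how they feel. Protocol 7.4.1.2 requires onset and resolution dates, and SAP 6 requires queries to be resolved before lock. This stands, and it keeps the point small. About four outpatient days remain (Day 11 to Day 15), all of them after tepotinib.

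**No column shift is written down.** Correct: the SAP has no assignment rule, so the shift depends on columns following imputed onset. That absence is itself a gap.

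**Worsening may be captured anyway.** Protocol 7.4.1.2 has unfavorable changes recorded as AEs, so a worsened condition can become a new record with its own onset. This is partial mitigation. The text does not say that worsening opens a new record, and it defers to eCRF conventions that are not among the documents.

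**The fallback can be read charitably.** Its beginning and end could mean dose and event. The example would then give 9 − 8 + 1 = 2. But no dose date is named, and the identical words one line earlier refer to the AE's own dates. SAP 9 also defines a correct relative day, though counted from the first administration in the trial.

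**A misplaced event would be noticed.** The SAP 15.1.1 overview has separate dabigatran-related and tepotinib-related rows and an overall column. A tepotinib-related event under dabigatran alone would stand out, and overall counts do not depend on the column. This limits the harm but does not correct the date.

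A reader might infer that all three rules push events into the dabigatran-alone column. The documents do not support that. The fallback changes only a derived interval. The missing worsening clause moves no event with a Period 2 onset: it leaves a worsened event under its earlier onset or outside the TEAEs.

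**Conclusion.** Two SAP rules give wrong values as written: the onset imputation for Period 2 events, and the missing-time fallback for days from dosing. The missing worsening clause is a secondary point, and matters only where an event that worsens on tepotinib is kept as one record.

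The 100% and 73% are shares of Period 2 events whose onset is undated or partial, not of all adverse events. The documents give no rate for such dates, and few are expected. The 73% assumes the minimum schedule and evenly spread start dates. A longer gap between periods would change the percentage but not the direction.

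A reader might also infer that each misplaced event costs the tepotinib column 5 percentage points. That is a ceiling for one row with 20 subjects in the denominator. It is reached only if the subject has no other event in that row. With 16 subjects the step would be 1/16 = 6.25 points. This is a minor item, worth correcting because it costs little and because the imputation error runs one way.

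**What to change.** Amend SAP 9 and 15.1 before database lock:

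1. State that an AE is assigned to the most recent treatment started before its onset, and which label covers Period 2 Days 1–7.
2. Impute a missing or partial onset to the start of the treatment period in which the AE was first recorded, limited by the known date parts and the resolution date. This avoids a blanket default in either direction.
3. Count an increase in severity after the first dose of a period as a TEAE of that period.
4. Correct the missing-time fallback for days from dosing to AE start date minus dose date, with one stated convention for the +1.

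The cost is a few sentences and minor programming. The tepotinib-period incidence may look slightly higher.
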